
Name of Sponsor:  Seqirus
	
Protocol number:  V130_14
	
Generic name of study vaccine(s):  Cell-Based Quadrivalent Subunit Influenza Virus Vaccine (QIVc)  Non-Influenza Vaccine

envelope-glycoprotein hemagglutinin (HA) of each of the four (4) influenza strains recommended by WHO for inclusion in the quadrivalent vaccine formulation for the influenza season corresponding to the season of conduct of study.
 
Vaccination schedule:
 
 
• Subjects ≥ 12 months with a previous influenza vaccination history: One dose of QIVc at Visit 1.
 
• Subjects ≥ 12 months without a previous influenza vaccination history and subjects 6 through 11 months: One dose of QIVc at Visit 1 followed by one dose of QIVc at Visit 2.
 
 
Comparator vaccine(s): Meningococcal Group C Polysaccharide Conjugate Vaccine (MenC vaccine, Neisvac-C, Pfizer) will be used as a comparator:
 
Vaccination schedule:
 
 
• Subjects ≥ 12 months with a previous influenza vaccination history: One dose of MenC vaccine at Visit 1.
 
• Subjects ≥ 12 months without a previous influenza vaccination history and subjects 6 through 11 months: One dose of MenC vaccine at Visit 1 followed by one dose of placebo at Visit 2.
 
 
All subjects aged 6 through 11 months at enrollment, regardless of treatment assignment, will receive a dose of the MenC vaccine at Visit 5.
		

Primary Efficacy Endpoint(s):
 
 
1. a. First occurrence of RT-PCR confirmed influenza, due to any influenza Type A and/or B virus regardless of antigenic match to the influenza strains selected for the seasonal influenza vaccine, occurring at > 14 days after the last vaccination and until the end of the influenza season, in association with protocol-defined ILI symptoms.
 
1. b. First occurrence of culture confirmed influenza, due to influenza Type A and/or B virus antigenically matched by ferret antigenicity testing to the strains selected for the seasonal influenza vaccine, occurring at > 14 days after the last vaccination and
 
		

Name of Sponsor:	Protocol number:	Generic name of study vaccine(s):
Seqirus	V130_14	Cell-Based Quadrivalent Subunit Influenza Virus Vaccine (QIVc)  Non-Influenza Vaccine

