12. Prior vaccination to prevent *Neisseria meningitidis* serogroup C disease or prior infection caused by this organism.
13. Received any other vaccines than influenza vaccine within 14 days (for inactivated vaccines) or 28 days (for live vaccines) prior to study vaccination or who are planning to receive any vaccine within 28 days after study vaccination.

Prior to receipt of second study vaccination, subjects must be evaluated to confirm that they are eligible for subsequent vaccination. If subjects meet any of the original exclusion criteria listed above or experienced severe tolerability issues after first study vaccination, they should not receive additional vaccinations. However, these subjects should be encouraged to continue study participation. This review of eligibility should be documented in the source document and the reason for not administering a scheduled study vaccine should be documented in the eCRF.

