### **4.3 Criteria for Delay of Vaccination**

There may be instances when individuals meet all eligibility criteria for vaccination yet have a transient infection which may warrant delay of vaccination: clinical signs of fever and/or body temperature elevation [ $\geq 38.0^{\circ}\text{C}$  ( $\geq 100.4^{\circ}\text{F}$ )) within 3 days prior to intended study vaccination], or use of antipyretics and/or analgesic medications within 24 hours prior to vaccination. Under such circumstances, a subject may be considered eligible for vaccination after the appropriate visit window has passed and inclusion/exclusion criteria have been rechecked and if the subject is confirmed to be eligible. In these instances, missing the visit window is not considered a protocol deviation.

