## **5.4 Procedure(s) related to Protocol Defined ILI episodes**

### **5.4.1 ILI Reminder Calls**

Active surveillance for per protocol defined ILI will be conducted weekly via a reminder call or during planned clinic visits, from Visit 1 until the end of the influenza season. The subject's parent(s)/LAR will be asked via a checklist to determine if symptoms of ILI are present. The purpose of the reminder call is to trigger an unscheduled visit and nasopharyngeal (NP) swab collection. During every reminder call, the subject's parent(s)/LAR will be instructed to report and visit the study site in case of an ILI episode as soon as possible (see [Section 5.4.2, Unscheduled Visit\(s\)](#)). The reminder calls are not intended to collect any clinical data. If during the ILI reminder call an ILI is identified, a visit to the study site should be planned as soon as possible, as described in [Section 5.4.2, Unscheduled Visit\(s\)](#). In countries, in the exceptional case where calls are not feasible, study site personnel may visit the subject's homes to inquire about signs and symptoms of illness in the subject.

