3.1 Primary Efficacy Endpoint(s)

Endpoints evaluating QIVc compared to a non-influenza vaccine:

- 1a. First occurrence of RT-PCR confirmed influenza, due to any influenza Type A and/or B virus regardless of antigenic match to the influenza strains selected for the seasonal influenza vaccine, occurring at > 14 days after the last vaccination and until the end of the influenza season, in association with protocol-defined ILI symptoms.
- 1b. First occurrence of culture confirmed influenza, due to influenza Type A and/or B virus antigenically matched by ferret antigenicity testing to the influenza strains selected for the seasonal influenza vaccine, occurring at > 14 days after the last vaccination and until the end of the influenza season, in association with protocol defined ILI symptoms.

Note: Last vaccination is defined as the last vaccination administered during the treatment period of the study.

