4.4 Full Analysis Set (FAS), Efficacy/ Immunogenicity Set

FAS, Efficacy

All subjects in the All Enrolled Set who are randomized, who received at least one dose of study vaccination and are evaluated for efficacy at more than 14 days after the last vaccination.

FAS, Immunogenicity

All subjects in the All Enrolled Set who are randomized, who received at least one study vaccination and provide evaluable serum samples at both baseline (Day 1) and 28 days after last vaccination (Day29/57).

Last vaccination is at Visit 1 for "previously vaccinated" subjects and at Visit 2 for "not previously vaccinated" subjects.

Statistical Analysis Plan – Final v2.0

Sponsor Name: Seqirus UK Limited
Sponsor Protocol ID: V130_14

In case of vaccination error, subjects in the FAS sets will be analyzed "as randomized" (i.e., according to the study vaccine a subject was designated to receive, which may be different from the study vaccine the subject actually received).

If a subject is unblinded during the study, he/she will be included in the FAS.

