6.5 Efficacy

6.5.1 Primary Efficacy Endpoints Analysis

The primary efficacy analysis will be based on the FAS Efficacy. Eligible subjects for FAS analysis are subjects who are randomized and received at least one study vaccine and will be analyzed according to their randomized study vaccine (intent-to-treat analysis). Absolute vaccine efficacy will only be assessed for RT-PCR confirmed influenza episodes (primary efficacy endpoint 1a) and culture confirmed antigenically matched influenza episodes (primary efficacy endpoint 1b) with first onset of illness occurring at > 14 days after the last vaccination was administered in the treatment period until the end of the influenza season. Additionally, the primary objective will be evaluated in PPS Efficacy.

Time-to-event methodology based on a proportional hazard model will be used for all efficacy analyses to estimate the hazard ratio (HR). Absolute vaccine efficacy (aVE) against first occurrence RT-PCR confirmed influenza cases will be determined using a standard formula: $aVE = 1 - HR$ where HR is the hazard ratio for RT-PCR influenza confirmed cases in the QIVc group versus the comparator group. The HR will be estimated by a proportional hazards regression model, described below. For which the following null (H0) and alternative (H1) hypotheses will be tested:

$$H_0: 1 - HR \leq 0 \text{ versus } H_1: 1 - HR > 0$$

where HR is a hazard ratio of QIVc versus comparator and VE is vaccine efficacy. For both primary efficacy objectives, the HR and the related 97.5% CI of HR, for onset of first RT-PCR confirmed influenza will be estimated by a proportional hazards regression model with treatment effect as a fixed effect and stratifying covariates as random effect:

$$h_i(t|X) = h_0(t) \exp(\beta^T X + b^T Z),$$

with t denoting time to the influenza, β is the effect of treatment group indicated by X , b is random effect (assumed as a multivariable random gaussian variable with zero mean and diagonal covariance matrix), Z is random effect covariate (reflecting randomization strata).

Subjects that did not experience an event during observation period (be > 14 days after last vaccination up to end of influenza season) and subjects that dropped out from the study during observational period will be censored (right censoring) at the last available date in the eCRF prior to the end of influenza season.

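### The SAP gives two conflicting definitions of last vaccination, so it is not settled whether an influenza case between the two doses is a primary event

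*Protocol*

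**What the plan says.** **Endpoint window.** Protocol Synopsis and 8.1.1.2 count a first case more than "14 days after the last vaccination and until the end of the influenza season, in association with protocol-defined ILI symptoms". The protocol does not say what last vaccination means for a two-dose child who misses dose 2.

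**First SAP definition.** A note to the primary endpoints in SAP 3.1, repeated for the secondary endpoints in 3.3, reads: "Last vaccination is defined as the last vaccination administered during the treatment period of the study". SAP 6.5.1 agrees, requiring onset more than "14 days after the last vaccination was administered in the treatment period".

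**Second SAP definition.** SAP 4.4 ties the term to the visit: Visit 1 for previously vaccinated "subjects and at Visit 2 for" those not previously vaccinated.

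**Primary analysis set.** SAP 4.4 admits to the efficacy FAS randomized subjects "who received at least one dose of study vaccination and are evaluated for efficacy at more than 14 days after the last vaccination". Dose 2 is not required. SAP 6.5.1 makes this set primary and repeats the analysis on the PPS.

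**Missed or late dose 2.** Protocol 4.2 says of children who fail the recheck before dose 2: "they should not receive additional vaccinations. However, these subjects should be encouraged to continue study participation". Protocol 4.3 covers those who "have a transient infection which may warrant delay of vaccination" and lets them be vaccinated after the visit window.

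**Surveillance between doses.** Protocol 5.4.1: "Active surveillance for per protocol defined ILI will be conducted weekly via a reminder call or during planned clinic visits, from Visit 1". Cases between the doses are therefore swabbed and known.

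**The concern.** Under the last-dose-administered definition, the event status of a case between the doses is fixed only after the case has occurred. The same illness is a primary event if dose 2 is later not given and is ignored if dose 2 is given. Because the illness may itself influence whether dose 2 follows, the extra cases are not a random sample. They also arise under one-dose protection, so they pull the estimate toward one-dose efficacy.

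Under the Visit 2 definition this does not happen. Two programmers working from the same SAP could therefore derive different FAS membership, event counts and VE. The RT-PCR case count also governs when the interim (96 or more) and final (191 or more) analyses may take place, so the ambiguity reaches the triggers as well as the estimate.

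**Working it through.** **1. The two definitions applied to one child.** Dose 1 is given on Day 1, and RT-PCR-confirmed ILI starts on Day 20, which is 19 days after dose 1.

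| What happens next | SAP 3.1, 3.3, 6.5.1 | SAP 4.4 |
|---|---|---|
| Dose 2 given on Day 29 | Clock starts Day 29; not an event | Not an event |
| Dose 2 never given | Clock starts Day 1; primary event | Not an event, though no date is given for a child without dose 2 |

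A case within 14 days of dose 1 counts under neither. One-dose children are unaffected.

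**2. The plan's own figures** (Protocol 8.5, SAP 2.3; one-sided alpha 0.0125 as in SAP 6.8). Schoenfeld events = (2.2414 + 1.2816)² / (0.25 × ln(HR)²).
- 1a, HR 0.60: 190.25, so 191; power at 191 is 90.1%.
- 1b, HR 0.50: 103.33, so 104; power at 104 is 90.2%.
- Evaluable subjects: 190.25/0.064 = 2,973 and 103.33/0.03 = 3,444; rounded up per arm, 1,487 and 1,723, as stated.
- Enrolled: 1,487/0.9 and 1,723/0.9 round up to 1,653 and 1,915 per arm, so 3,306 and 3,830, as stated.

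These figures are not in dispute.

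**3. Size for endpoint 1a.** From the documents: 1,487 per arm, 8% comparator attack rate, VE 40%, and a 28-day dose interval with a +7-day window. The countable gap W is therefore 28 − 14 = 14 to 35 − 14 = 21 days. Assumed: all children on two doses, constant hazard, attack rate accrued over L = 120 or 180 days, a share s = 5% to 50% of inter-dose cases then missing dose 2, and one-dose VE (VE1) of 0% to 40%.

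- Daily hazard λ = −ln(0.92)/L
- Comparator inter-dose cases c = 1,487 × (1 − exp(−λW))
- QIVc inter-dose cases q = 1,487 × (1 − exp(−λW(1 − VE1)))
- HR = (1,487 × 0.048 + s·q) / (1,487 × 0.08 + s·c)
- Power = Φ(−ln(HR) × √(191/4) − 2.2414)

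| L | W | VE1 | s | Inter-dose cases, comparator / QIVc | Counted | VE | Power at 191 |
|---|---|---|---|---|---|---|---|
| 180 | 14 | 20% | 5% | 9.6 / 7.7 | 0.5 / 0.4 | 39.9% | 90.0% |
| 180 | 14 | 20% | 25% | 9.6 / 7.7 | 2.4 / 1.9 | 39.6% | 89.3% |
| 180 | 14 | 0% | 25% | 9.6 / 9.6 | 2.4 / 2.4 | 39.2% | 88.5% |
| 120 | 21 | 40% | 50% | 21.5 / 13.0 | 10.8 / 6.5 | 40.0% | 90.1% |
| 120 | 21 | 20% | 50% | 21.5 / 17.3 | 10.8 / 8.6 | 38.3% | 86.4% |
| 120 | 21 | 0% | 50% | 21.5 / 21.5 | 10.8 / 10.8 | 36.7% | 82.0% |

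Last row in full: (71.4 + 10.8)/(119.0 + 10.8) = 0.633, so VE is 36.7%; Φ(0.457 × 6.910 − 2.241) = Φ(0.915) = 82.0%. This is a ratio of cumulative counts, not a Cox risk-set calculation.

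**4. Simulation** (1,500 runs per scenario, 1,487 per arm, VE 40%, 14-day gap, 3% missing dose 2 for unrelated reasons). The clock from the last dose given is compared with a fixed clock from scheduled dose 2.
- One-dose VE 20%, omission after 5%, 25% and 50% of inter-dose cases: mean VE 39.4%, 39.3% and 39.0%, against 39.6%, 39.7% and 39.7%.
- One-dose VE 0%, omission after 50%: 37.8% against 39.2%.
- No vaccine effect: one-sided rejection rate 0.9% to 1.3% against the nominal 1.25% (Monte Carlo error about 0.3 points). This includes a scenario with unrelated missed doses of 3% in one arm and 10% in the other.

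**The case against.** **The first definition may have another purpose.** The SAP 3.1 note can be read as keeping the Visit 5 MenC dose, given to children enrolled at 6 through 11 months, from restarting the clock. SAP 4.4 would then supply the rule for two-dose children. This is plausible, but the SAP 4.4 sentence directly follows the immunogenicity FAS definition, so its reach to efficacy is arguable. The note is attached to the primary endpoints and speaks of the dose administered. The conflict stands. What does not stand is the inference that the last dose given is the settled rule; SAP 4.4 says otherwise.

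**Illness mostly leads to delay, not omission.** A reader might infer from the fever rules that many infected children lose dose 2. The documents do not support that. Exclusion 1 allows enrolment to be considered once fever has been absent for 72 hours, and Protocol 4.3 provides for later vaccination. Exclusion 11 concerns influenza before informed consent, so by its wording an inter-dose case does not bar dose 2. No document gives an omission rate. This objection is correct and keeps the likely size low.

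**Bias between arms.** A reader might also infer differential bias or false positives. The trial is observer-blind, nothing suggests that omission differs by arm, and the simulation showed no inflation. That inference is dropped.

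**The PPS already checks this.** SAP 4.5 requires dosing as scheduled and gives a confirmed case between first vaccination and 14 days after last vaccination as an example of an exclusion. That is a real safeguard, but the FAS is primary and has no equivalent rule.

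**Conclusion.** The concern holds as a conflict between two SAP definitions in a rule that decides which cases are primary events. Under one of them, event status in the FAS depends on what happens after the case.

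The likely effect is small and toward one-dose efficacy. VE of 36.7% and power of 82% need every child on two doses, one-dose VE of 0%, a 21-day gap, a 120-day season and half of the inter-dose cases missing dose 2. If one-dose VE equals 40% there is no effect. In simulation the difference between the two clocks was 0.2 to 0.7 percentage points of VE at one-dose VE 20%, and 1.4 points at one-dose VE 0% with half missing dose 2. Part of the shortfall from 40% remains under a fixed clock, so not all of it is due to the definition.

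The share of two-dose children, the omission rate and one-dose VE are assumptions, and the size was worked out for 1a only. The planned 191 and 104 events are unchanged. The point should be settled before unblinding because it affects the event count, not because a large bias has been shown.

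**What to change.** Reconcile SAP 3.1, 3.3 and 6.5.1 with SAP 4.4, and align Protocol 8.1.1.2 and 8.1.2.2. For the FAS, use one clock that does not depend on whether or when dose 2 was given. For example, for all not-previously vaccinated children in both arms:

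- Open the window more than 14 days after the scheduled Visit 2 date (Visit 1 + 28 days, or the end of its +7-day window).
- Apply the same date to the FAS condition of being evaluated more than 14 days after last vaccination.
- State that earlier confirmed cases are not 1a or 1b events, and how those children are handled afterwards.
- Keep the actual-dose clock for the PPS.

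A fallback to the scheduled date only when dose 2 is missed is not enough. Scheduled Visit 2 is Day 29, so that fallback window opens after Day 43. A child whose dose 2 is delayed and who has a case on Day 46 would not count if dose 2 is given on Day 55, but would count if it never is.

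A supportive FAS analysis of all first RT-PCR cases from Visit 1 is optional; the swabs are already collected.

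The cost is a sentence in each affected section and one derivation change, plus one table if the optional analysis is added. The downside is a little lost person-time for dose-1-only children and, for children with a late dose 2, some included time before full protection. No dose, schedule, visit or swab changes.

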**Study Event**

**References**

- a) In the exceptional case where calls or clinic visits are not feasible in some countries, study site personnel may visit the subject's homes to inquire about signs and symptoms of illness in the subject, collect a NP swab specimen or perform other study assessments (see Section 5 Study Procedures), when agreed upon by the Sponsor and in line with country specific requirements and/or regulations.
  - b) Study completion visit is a call for subjects aged 12 months and older at enrollment, and is a clinic visit for subjects 6 through 11 months at enrollment
  - c) A subject diary reminder call is a call approximately 2 days after vaccination
  - d) Performed at End of Influenza Season but at least 180 days after last vaccination
  - e) Informed Consent Form can be collected before Study day 1
  - f) Procedures that should be completed before vaccination
  - g) Blood draws are only applicable for subjects randomized into the immunogenicity sub-set. Collect blood samples before vaccination
  - h) ILI Symptom Assessment and Documentation Training includes use of ILI Booklet to be completed if an ILI occurs
  - i) Performed until End of Influenza Season
- \*Should an ILI be identified and a NP swab obtained, it is recommended to postpone the study completion visit, to allow for the ILI follow-up visit to occur (see Section 5.5, Study Completion)

**Table 1.3 Time and Events Table – Unscheduled visit(s) related to a protocol defined ILI episodea**

	Visit Type	Unscheduled Clinic Visit b	ILI Follow-up Call c,*
	ILI Onset Day	1 d	+ 30
	Visit Number	n/a	n/a
	Visit Window (Days)	0 to +6	0 to +7
Study Event	References		
Efficacy			
ILI Booklet Review and Collection	Section 5.4.2	√	
Assess ILI symptoms	Sections 5.4.3 and 7.2	√	√
ILI Nasopharyngeal Swab Collection d	Sections 3.5 and 5.4.2	√ d	
Assess Relevant Medications and Vaccinations	Sections 5.1.2, 5.4.3 and 6.5	√	√
Assess Medically-Attended AEs e	Sections 5.4.3 and 7.1.2	√ e	√ e
Physical Examination	Sections 5.1.2 and 5.3.1	√	
ILI Symptom Assessment and Documentation Training f	Section 5.2.5	√ f	

Visit Type	Unscheduled Clinic Visit b	ILI Follow-up Call c,*
ILI Onset Day	1 d	+ 30
Visit Number	n/a	n/a
Visit Window (Days)	0 to +6	0 to +7

Study Event	References

a) Influenza-like illness (ILI) is defined by the presence of a temperature <math>\geq 37.8^{\circ}\text{C}</math> (<math>\geq 100.0^{\circ}\text{F}</math>) and at least one of the following symptoms on the same day: cough, sore throat, nasal congestion, rhinorrhea, earache or ear discharge
 
b) In the exceptional case that the subject cannot visit the study center, a home visit can be made
 
c) In countries, in the exceptional case where calls are not feasible, study site personnel may visit the subject's homes to inquire about signs and symptoms of illness in the subject.
 
d) Subject will be asked to come to the study site within the first 24 hours or as soon as possible following ILI onset to ensure optimal viral yield
 
e) A "medically-attended adverse event" is an adverse event requiring hospitalization, or emergency room visit, or visit to/by a health care provider. See section Definitions.
 
f) ILI Symptom Assessment and Documentation Training includes use of ILI Booklet to be completed if an ILI occurs
 
*Should an ILI be identified and a NP swab obtained, it is recommended to postpone the study completion visit, to allow for the ILI follow-up visit to occur (see Section 5.5, Study Completion)
	

## LIST OF ABBREVIATIONS

AE	Adverse Event
BLA	Biologics License Application
CBER	Center for Biologics Evaluation and Research
CDC	Centers for Disease Control and Prevention
CHMP	Committee for Medicinal Products for Human Use
CI	Confidence Interval
CRF	Case Report Form
CRO	Contract Research Organization
CSR	Clinical Study Report
DMC	Data Monitoring Committee
EC	Ethics Committee
eCRF	Electronic Case Report Form
EDC	Electronic Data Capture
EMA	European Medicines Agency
FAS	Full Analysis Set
FDA	Food and Drug Administration
GCP	Good Clinical Practices
GMR	Geometric Mean Ratio
GMT	Geometric Mean Titer
HA	Hemagglutinin
HI	Haemagglutination Inhibition
HIPAA	Health Insurance Portability and Accountability Act
HR	Hazard ratio
IA	Interim Analysis
IB	Investigator's Brochure
ID	Identification
ICF	Informed Consent Form
ICH	International Conference on Harmonisation
ICU	Intensive Care Unit
ILI	Influenza-Like Illness
IM	Intramuscular
IRB	Institutional Review Board
IRT	Interactive Response Technology
LAR	Legally Acceptable Representative(s)
LL	Lower Limit
MDCK cells	Madin Darby Canine Kidney cells
MedDRA	Medical Dictionary for Regulatory Activities
MenC	Meningococcal (Group C) Conjugate Vaccine

MN	Microneutralization
NA	Neuraminidase
NP	Nasopharyngeal
NH	Northern Hemisphere
NOCD	New Onset of Chronic Disease
PCR	Polymerase Chain Reaction
PDCO	Paediatric Committee
PFS	Pre-filled syringes
PIP	Paediatric Investigation Plan
PP	Per Protocol
PPAS	Per Protocol Analysis Set
PRO	Patient Reported Outcome
PV	Pharmacovigilance
QIVc	Cell-derived Quadrivalent Influenza Vaccine
QIV	Quadrivalent Influenza Vaccine
Qs	Quantity sufficient
RT-PCR	Reverse Transcription Polymerase Chain Reaction
SAE	Serious Adverse Event
SAP	Statistical Analysis Plan
sBLA	Supplement Biologics License Application
SC	Seroconversion
SDA	Source Data Agreement
SH	Southern Hemisphere
SOP	Standard Operating Procedure
SPC	Summary of Product Characteristics
TIV	Trivalent Influenza Vaccine
USPI	United States Patient Information leaflet
VE	Vaccine Efficacy
WHO	World Health Organization

